4.1.8 Visit Dates

For each visit, the date recorded by the Investigator in the eCRF (variable SVSTDTC in the SDTM SV domain) will be considered as the visit date in all the algorithms and the listings.

4.1.9 Date of First/Last IMP Dose

The date of first IMP dose is the earliest date of IMP dose considering both the eCRF and the recordings from the CCI logging system.

The date of last IMP dose is derived as follows. Where CCI data is available for the subject, the date of last IMP dose will be defined as the latest date from the CCI logging system, with the following exception. Due to the Covid-19 pandemic, for some subjects, Visit 7 was split into a remote phone call (at the scheduled time of treatment completion), followed by an in-clinic visit (for the purpose of collecting pre-dose and post-dose spirometry data to test for bronchospasm). In such cases, the scheduled study treatment period was completed at the time of the remote Visit 7 phone call, but an additional IMP dose was given at the time of the in-clinic Visit 7. In these circumstances, the latest date from the CCI logging system will be compared to the penultimate date from the CCI logging system and, if the latest date is more than 14 days after the penultimate date (latest date – penultimate date >14), the CCI logging system data will be used taking into consideration the penultimate IMP dose as the date of last IMP dose. The date of last IMP dose will be defined as the date of last IMP administration as entered on the End of Study eCRF form only when CCI data is unavailable.

Any inconsistency between eCRF and CCI logging system data will be discussed before the database lock.

4.1.10 Data Re-Allocation

Data collected at the early termination visit (when used) for discontinued subjects will not be re-allocated. Early termination data will not be moved in the database, however, statistical programming will allocate this visit as Visit 7 within the Analysis Data Model (ADaM) datasets.

Potential issues of the approach defined above and other decisions regarding data re-allocation will be evaluated during the blind review of the data and documented in the Blind Data Review and Analysis Sets Report.

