4.1.11 Exclusion of Data from the Statistical Analysis

If a subject received the incorrect treatment after being treated with the correct one, all the data collected after the date of the wrong treatment dispensing will be reported in listings and flagged, but not included in the statistical analysis on the IIT, mITT, Safety and PP populations.

CONFIDENTIAL

Sponsor:	Zambon S.p.A.	Protocol Number:	Z7224L01
----------	---------------	------------------	----------

Where not stated differently, assessments conducted at an early termination visit and unscheduled assessments will not be considered in the statistical analysis, but will be listed only.

Only NCFB pulmonary exacerbations with a start date \geq date of first IMP dose and \leq date of treatment completion/discontinuation will be considered in the analysis.

In case of data excluded from the statistical analysis (in the situations described above but also in other cases, for example: spirometry tests excluded due to technical issues, or assessment not done), the derived variables based on these data will not be calculated. For example, the change from baseline to Visit 5 will not be calculated if the measurement at Visit 5 is excluded from the statistical analysis, or all the changes from baseline will not be calculated if the measurements pre-dose are excluded.

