4.7.6.2 CCI

For the CCI the following weights will be calculated:

- CCI
- CCI
- CCI
- CCI

Each domain score will be calculated as follows:

- CCI

The total score will be calculated as follows:

- CCI

Missing data will be dealt with as described in CCI CCI

Weights of each item and other details for calculation are reported in CCI CCI

The CCI and CCI CCI) assessed at Visits 3 - 7 (End of Treatment) will be summarised by treatment group using descriptive statistics including 25th and 75th percentiles. Results for absolute changes from baseline will also be reported. Due to CTP amendments and to the corresponding changes in the procedures schedule, not all the subjects have undergone the same sequence of assessments. All the values collected will be summarised jointly. Considering the presence of a stratified and permuted blocks randomisation list no imbalance between treatments is expected.

Change from baseline in CCI total score at Visit 3, Visit 4, Visit 5, Visit 6 and Visit 7 will be analysed using a linear mixed model for repeated measures including treatment, visit, treatment-by-visit interaction, use of stable concomitant therapy with oral macrolides and pooled site, i.e. country, as detailed in Section 4.9.1, as fixed effects and baseline value as covariate. An unstructured covariance matrix will be assumed and the Kenward-Roger adjustment will be used for the degrees of freedom. The least square means in each treatment group, the least square mean differences between treatments, their 95% CIs and associated p-values overall and at each visit will be estimated by the model. The OBSMARGINS option will be used. A two-sided p-value of <0.05 for the overall mean difference between treatments will be considered statistically significant.

The above summaries/analyses will be performed using the mITT and PP Populations. Results for the PP Population will be considered as supportive.

CONFIDENTIAL

Sponsor:	Zambon S.p.A.	Protocol Number:	Z7224L01
----------	---------------	------------------	----------

Notes:

- While for Visit 2, Visit 4, Visit 5, Visit 6 and Visit 7 the 3-month version of the CCI is used, for Visit 2 data are collected for the 4-week version. Visit 2 scores will not be included in the linear mixed model analysis but they will be included in the descriptive analysis.

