Change from baseline in each CCI [REDACTED] domain score will be analysed using a linear mixed model for repeated measures including treatment, visit, treatment-by-visit interaction, use of stable concomitant therapy with oral macrolides and pooled site, i.e. country, as detailed in CCI [REDACTED] [REDACTED], as fixed effects and baseline value as covariate. An unstructured covariance matrix will be assumed and the Kenward-Roger adjustment will be used for the degrees of freedom. The least square means in each treatment group, the least square mean differences between treatments, their 95% CIs and associated p-values overall and at each visit will be estimated by the model. The OBSMARGINS option will be used. A two-sided p-value of <0.05 for the overall mean difference between treatments will be considered statistically significant.

The above summaries/analyses will be performed using the mITT Population.

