4.11 Missing Values – Missing Visits

The validity of the negative binomial model planned for the primary efficacy analysis of the mean annual NCFB exacerbation rate relies on the MAR assumption.

The validity of the log-rank test planned for the CCI and the supportive Cox proportional hazard regression model relies on the uninformative censoring assumption.

CCI analyses will be conducted to investigate the robustness of the conclusions of these analyses. A detailed description of these analyses is provided in Sections 4.7.4.2 and 4.7.6.1.

In the analysis of CCI total score and CCI domain scores, linear mixed models for repeated measures will be used to handle missing data. Under the MAR assumption, these models provide an unbiased estimate of the treatment effect that would have been observed if all subjects had continued on treatment [7].

The analysis of covariance model for the CCI will include only complete cases. CCI analyses might be added during the blind review meeting if the amount of missing data makes it reasonable for further investigations of their influence on the overall study results. Decisions will be documented in the Blind Data Review and Analysis Sets Report.

Unless stated otherwise, there will be no imputation of missing values and only observed data will be included in the summaries.

The number of subjects with missing data will be presented under a “Missing” category. Unless otherwise stated, missing values will be included in the denominator count when computing percentages.

When continuous data are being summarised, only the non-missing values will be evaluated for computing summary statistics.

In order to calculate the duration of last usage of colistimethate sodium/colistin and the time from last administration of colistimethate sodium/colistin, the following rules will be applied for partial dates of start and stop date of last administration of colistimethate sodium/colistin:

For the start date:

- if only the day is missing, the first day of the month will be assumed;
- if the day and the month are missing, then the date will not be imputed and the time/duration will be classified as “Not Evaluable”.

For the stop date:

- if only the day is missing, the last day of the month will be assumed;
- if the day and the month are missing, then the date will not be imputed and the time/duration will be classified as “Not Evaluable”.

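### SAP 4.1.10 labels early-termination visits as Visit 7 and is not reconciled with 4.1.11, so it is unsettled whether withdrawal-time values are analysed as month-12 outcomes

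*SAP*

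**What the plan says.** SAP 4.1.10 (Data Re-Allocation) opens: "Data collected at the early termination visit (when used) for discontinued subjects will not be re-allocated". It adds that the data stay in place in the database, but that "statistical programming will allocate this visit as Visit 7 within the Analysis Data Model (ADaM) datasets". The next paragraph defers: "Potential issues of the approach defined above and other decisions regarding data re-allocation will be evaluated during the blind review of the data", with decisions recorded in the Blind Data Review and Analysis Sets Report.

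SAP 4.1.11 (Exclusion of Data) says: "Where not stated differently, assessments conducted at an early termination visit and unscheduled assessments will not be considered in the statistical analysis". Such assessments go to listings only, and variables derived from excluded data are not computed.

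The models that use Visit 7 are in SAP 4.7.6.2, where the "total score at Visit 3, Visit 4, Visit 5, Visit 6 and Visit 7 will be analysed using a linear mixed model for repeated measures", and in SAP 4.7.6.9, where each "domain score will be analysed using a linear mixed model for repeated measures including treatment, visit, treatment-by-visit interaction". Both judge significance at two-sided 0.05 on the overall mean difference. Neither section, nor the example code in 4.14, gives a visit window, a filter or a rule for early-termination values. SAP 4.11 justifies these models: "Under the MAR assumption, these models provide an unbiased estimate of the treatment effect" that would have been seen had everyone stayed on treatment.

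Protocol 8.5 places Visit 7 at 12 months ± 1 week. Protocol 14 asks withdrawn subjects to attend an early visit where possible.

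**The concern.** A programmer reading 4.1.10 and 4.1.11 together cannot tell whether an early-termination score belongs in the Visit 7 analysis record. If the label is taken at face value, a score recorded at month 2 becomes a month-12 outcome. The extreme case is built into the design. Subjects with bronchospasm, or an FEV₁ fall above 15%, after the first dose are withdrawn (Protocol 8.2 and 14) but stay in the mITT population because they received a dose (SAP 3.5.2). An early visit by such a subject would supply a near-baseline value under a month-12 label.

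For the mixed models this changes what is estimated. The 4.11 rationale needs the months after withdrawal to be treated as missing. A mis-timed value fills the Visit 7 cell and distorts the visit correlations that the model uses to handle gaps elsewhere.

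Several Visit 7 summaries are exposed too. These include laboratory, vital-sign and ECG results, visit attendance (SAP 4.3) and the Visit 7 points on the Addendum's line plots. SAP 4.8.3 shows the problem well: it reports susceptibility at Visit 7 without imputation and gives a separate table of last available results. Relabelling blurs that distinction.

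**Working it through.** **Step 1: the text side by side.**
- 4.1.10, first sentence: no re-allocation.
- 4.1.10, later: the visit is Visit 7 in the analysis datasets.
- 4.1.11: listing only, unless stated differently.

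If 4.1.10 is the stated difference, it covers every early-termination visit, and the early-termination part of 4.1.11 has nothing left to govern. If it is not, the Visit 7 label has no clear analytic purpose. Elsewhere the SAP states its exceptions locally: the shift tables in 4.8.4 to 4.8.7 explicitly take in unscheduled visits. The mixed-model sections contain no such statement for early-termination values.

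**Step 2: what is outside the problem.** The primary negative binomial model (4.7.4) uses event counts with a follow-up-time offset. The ANCOVA in 4.7.6.3 tests the change to Visit 3. Neither depends on the Visit 7 label.

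**Step 3: how many subjects.** The plan's drop-out figure (SAP 3.9) is about 20%. It reproduces: 170 / (1 − 0.20) = 212.5, so 213, against the stated 210 per arm. Recruitment ended at 377, so at most 377 × 0.20 ≈ 75 subjects could have a relabelled value. At 10% it is about 38. At 22.9%, reading the step from 145 to 188 per arm as a drop-out allowance (1 − 145/188), it is about 86.

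**Step 4: illustrative dilution.** These assumptions are not in the documents: the effect grows linearly from 0 to D at month 12; withdrawal is uniform over the year, so the average effect at withdrawal is 0.5D; a fraction a of withdrawals has an early visit; the Visit 7 mean is a simple mixture; visits are weighted equally.
- Share of Visit 7 values from early termination: w = d·a / (d·a + 1 − d), where d is the withdrawal rate.
- Visit 7 effect relative to the true month-12 effect: V = 1 − 0.5w.
- Overall difference relative to true: (S − 1 + V) / S. S is the sum of the true visit effects in units of D. S = 2.577 for Visits 3–7 (28/365 + 0.25 + 0.5 + 0.75 + 1) and S = 2.5 for Visits 4–7, the set in the example code.

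| d | a | w | V | overall, 5 visits | overall, 4 visits |
|---|---|---|---|---|---|
| 10% | 50% | 0.053 | 0.974 | 0.990 | 0.989 |
| 10% | 100% | 0.100 | 0.950 | 0.981 | 0.980 |
| 20% | 50% | 0.111 | 0.944 | 0.978 | 0.978 |
| 20% | 100% | 0.200 | 0.900 | 0.961 | 0.960 |
| 22.9% | 50% | 0.129 | 0.935 | 0.975 | 0.974 |
| 22.9% | 100% | 0.229 | 0.886 | 0.956 | 0.954 |

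**Step 5: earlier withdrawal.** If all of the 20% withdraw near month 4.5 and all have a visit, the Visit 7 loss is 0.20 × (1 − 4.5/12) = 0.125D. Over four visits that is 0.125 / 2.5 = 5% of the overall difference.

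**Step 6: other effect shapes.** A constant effect gives no timing dilution. A waning effect makes the Visit 7 contrast too large. Withdrawal related to outcome, or differing between arms, is not covered by these figures and could act either way.

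**The case against.** The case against is substantial.

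- **It is not a plain breach.** A reader might infer that 4.1.10 violates the SAP's own exclusion rule. The qualifier that opens 4.1.11 prevents that conclusion: the rule is a default, and 4.1.10 can be read as an exception. Within 4.1.10, the contrast between the collected database and the analysis datasets is also intelligible. What stands is that the reader has to guess.
- **Entry into the models is not stated.** A visit label is not an inclusion rule, and a value could carry the Visit 7 label and still only be listed. The final handling may be in the blind-review report, which is not among the documents. What stands is that deferral does not settle which data enter the tested secondary endpoints; the SAP should.
- **It is not last-value-carried-forward.** A reader might call it that, but nothing is imputed. An observed value may receive the wrong nominal time. Skipped visits, and withdrawals with no early visit, remain missing and are still handled under the missing-at-random assumption.
- **The Visit 7 loss is not the tested loss.** The 12.5% figure applies to Visit 7 alone, while significance is judged on the overall difference. It also needs every withdrawal to attend a visit that the protocol asks for only where possible.
- **Position in the hierarchy.** The list in 4.7.5 is redacted, so the consequences for later tests cannot be traced.

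**Conclusion.** The point holds as an unreconciled rule with a conditional consequence. 4.1.10 is at odds with itself on re-allocation and is not squared with 4.1.11. If the label is applied as written, withdrawal-time values are modelled as month-12 values, contrary to the reasoning in 4.11.

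In the illustration, the Visit 7 loss is about 6–10% at 20% withdrawal, or 12.5% if all withdraw near month 4.5. The tested overall difference loses about 2–4%, rising to 5% in that earlier-withdrawal case. These figures rest on an assumed growing effect and assumed attendance at early visits; neither size nor direction is established by the documents.

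The reach is limited to the secondary questionnaire models, the Visit 7 safety summaries and related displays. A reader might infer a threat to the primary result, but the documents do not support it. The point should be corrected because the ambiguity is avoidable and concerns which data enter tested endpoints.

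**What to change.** Delete the blanket Visit 7 allocation and put one rule in both 4.1.10 and 4.1.11:
- Assign each early-termination assessment to the scheduled visit whose window contains its study day.
- If a scheduled assessment already exists in that window, the scheduled one takes precedence.
- Otherwise keep the assessment as a separate early-termination record, outside by-visit models and tables.

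The SAP defines no analysis windows, so the rule must name them; the protocol's ± 1 week visit windows are one option.

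As a planning change this costs a few sentences and one ADaM derivation. It is no longer only that, because the SAP Addendum (2.2) records that the database is locked and the study unblinded. The clinical trial report should therefore state which handling was used, give the number of early-termination values in Visit 7 by arm, and report the other handling as a sensitivity analysis marked post hoc, as SAP section 1 requires. The added work is a rerun of the questionnaire mixed models and the affected Visit 7 tables.

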4.1.11 Exclusion of Data from the Statistical Analysis

If a subject received the incorrect treatment after being treated with the correct one, all the data collected after the date of the wrong treatment dispensing will be reported in listings and flagged, but not included in the statistical analysis on the IIT, mITT, Safety and PP populations.

CONFIDENTIAL

Sponsor:	Zambon S.p.A.	Protocol Number:	Z7224L01
----------	---------------	------------------	----------

Where not stated differently, assessments conducted at an early termination visit and unscheduled assessments will not be considered in the statistical analysis, but will be listed only.

Only NCFB pulmonary exacerbations with a start date \geq date of first IMP dose and \leq date of treatment completion/discontinuation will be considered in the analysis.

In case of data excluded from the statistical analysis (in the situations described above but also in other cases, for example: spirometry tests excluded due to technical issues, or assessment not done), the derived variables based on these data will not be calculated. For example, the change from baseline to Visit 5 will not be calculated if the measurement at Visit 5 is excluded from the statistical analysis, or all the changes from baseline will not be calculated if the measurements pre-dose are excluded.

4.1.12 Listings

All data collected will be presented in the listings.

4.2 Interim Analysis

No interim analysis is planned for this study.

4.2.1 Data CCI

Due to the impact of Covid-19 during the conduct of the study, the Sponsor has established a CCI Committee CCI to evaluate the impact of decisions made CCI on the integrity of the study data. Although the CCI will only review blinded data, the CCI will advise if additional CCI analyses may be needed as a result of this pandemic. In addition, the CCI will review blinded pulmonary exacerbation data to determine whether or not events have been correctly assigned as meeting protocol-defined criteria. The CCI may recommend that sites reconsider their classification of pulmonary exacerbations as meeting the protocol-defined criteria or not (as well as re-examine the duration of the event based on the existing eCRF data), however, the ultimate decision will remain that of the Principal Investigator at each site.

For clarification purposes (and the generation of relevant data queries to sites), a further clarification to the protocol definition for pulmonary exacerbations has been provided as follows:

- the presence of 3 or more pre-defined symptoms / signs¹ within any 24-hour period²
- and
- the episode of exacerbation lasted for at least 24 hours³
- and
- in the opinion of the Investigator, the subject required and started treatment with systemic antibiotics

Explanatory notes:

¹The pre-defined symptoms / signs are: increased cough; increased sputum volume and / or consistency; increase sputum purulence; new or increased haemoptysis; increased wheezing; increased dyspnoea; increased fatigue / malaise; episodes of fever ($\geq 38^{\circ}\text{C}$ or $\geq 100.4^{\circ}\text{F}$).

CONFIDENTIAL

Sponsor:	Zambon S.p.A.	Protocol Number:	Z7224L01
----------	---------------	------------------	----------

² The pre-defined symptoms / signs need to occur within the same 24-hour period (and this defines the start date of the Protocol-Defined Exacerbation) but do not need to be present at exactly the same time.

³ The overall episode of exacerbation needs to last at least 24 hours, but individual symptoms / signs can last less than 24 hours (for example, a temperature).

4.3 Disposition of Subjects

The number of subjects screened and the number of screen failures will be presented (overall). All screened subjects will be included. Re-screened subjects will be counted twice in the number of screened subjects. The number of re-screened subjects will be presented.

The number and percentage of randomised subjects who completed the study, withdrew from the study after randomisation and the number and percentage of subjects with each reason for withdrawal from the study will be presented by treatment group for the ITT population. Summaries of enrolled subjects will be reported overall and by country. These will include a presentation of country, number of subjects randomised and number of subjects who completed the study for the ITT population.

The number and percentage of subjects at Visit 2, who attended Visits 3, 4, 5, 6 and 7 and who had a follow-up call will be presented by treatment group and overall for the mITT Population. Time to completion/discontinuation from the study (days) will be summarised by descriptive statistics and calculated as (date of completion/discontinuation – date of first IMP dose).

The number and percentage of screened subjects who had any inclusion/exclusion criteria deviation as detailed in the eCRF will be reported. Results will be presented also for each criterion.

Protocol deviations affecting the efficacy analyses and protocol deviations specifically related to the COVID-19 pandemic will also be summarised for the Enrolled Population. The number and percentage of subjects included in each analysis population will be presented overall and by treatment group.

